12 MEASUREMENT OF EFFECT

Although the clinical benefit of birinapant has not yet been established, the intent of offering this treatment is to provide a possible therapeutic benefit, and thus the patient will be carefully monitored for tumor response and symptom relief in addition to safety and tolerability. Patients with measurable disease will be assessed by standard criteria. For the purposes of this study, patients should be re-evaluated at 3, 6, 9, 12 and 24 months after completion of the protocol treatment.

12.1 Antitumor Effect – Solid Tumors

Patients will be evaluated at baseline and at 3, 6, 9, 12 and 24 months after completion of the protocol treatment. The details of timing and imaging types are specified in Study Calendar in Section 11.

Response and progression will be evaluated in this study using the new international criteria proposed by the revised Response Evaluation Criteria in Solid Tumors (RECIST) guideline (version 1.1)(25). Changes in the largest diameter (unidimensional measurement) of the tumor lesions and the shortest diameter in the case of malignant lymph nodes are used in the RECIST criteria.

12.1.1 Definitions

Evaluable for toxicity. All patients will be evaluable for toxicity from the time of their first treatment with birinapant.

Evaluable for objective response. Only those patients who have measurable disease present at baseline, have received at least one cycle of therapy, and have had their disease re-evaluated will be considered evaluable for response. These patients will have their response classified according to the definitions stated below. (Note: Patients who exhibit objective disease progression prior to the end of cycle 1 will also be considered evaluable.)

Evaluable Non-Target Disease Response. Patients who have lesions present at baseline that are evaluable but do not meet the definitions of measurable disease, have received at least one cycle of therapy, and have had their disease re-evaluated will be considered evaluable for non-target disease. The response assessment is based on the presence, absence, or unequivocal progression of the lesions.

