6 TREATMENT PLAN

This is an open-label Phase I study enrolling patients in 2 cohorts: dose escalation cohort and expansion cohort.

Treatment will be delivered in 2 cycles, lasting 3 weeks each.

Birinapant will be administered IV on Days 2 and 9 of each cycle in combination with IMRRT starting on Day 1 of cycle 1 and continuing for 5 days a week (Monday-Friday) for 6 weeks.

If a dose of birinapant is missed due to a scheduled holiday, inclement weather, personal emergency, or other reasons, then it should be given the following day.

If daily radiation treatment is missed due to a scheduled holiday, inclement weather, personal emergency, or other reasons, then the day(s) and fraction(s) missed should be added at the end of the course to complete the total planned treatment dose (e.g. 60Gy).

Patients in the dose escalation cohort will be treated with escalating doses of birinapant with IMRRT until MTD of birinapant in combination with IMRRT is established.

Patients in expansion cohort will be treated with the estimated MTD of birinapant in combination with IMRRT.

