6.5 Duration of Therapy

In the absence of treatment delays due to adverse event(s), treatment may continue for 2 cycles or until one of the following criteria applies:

- Disease progression
- Intercurrent illness that prevents further administration of treatment
- Unacceptable adverse event(s) as described in Sections [6.2](#) and [7](#).
- Patient decides to withdraw from the study
- General or specific changes in the patient's condition that render the patient unacceptable for further treatment in the judgment of the investigator

- Clinical progression
- Patient experiences a grade 4 non-hematologic toxicity or any grade 3 toxicity not returning to \leq grade 1 after 2 weeks of supportive care. The patient may continue with IMRRT but will be taken off birinapant.
- Patient non-compliance with <80% of birinapant doses (less than 3 out of the 4 total doses) or with scheduled appointments for investigational treatment that may affect treatment outcome, per PI discretion.
- Pregnancy
 - All women of child bearing potential will be instructed to contact the investigator immediately if they suspect they might be pregnant (e.g., missed or late menstrual period) at any time during study participation.
 - The investigator must immediately notify CTEP in the event of a confirmed pregnancy in a patient participating in the study.
- Termination of the study by sponsor
- The drug manufacturer can no longer provide the study agent

The reason(s) for protocol therapy discontinuation, the reason(s) for study removal, and the corresponding dates must be documented in the Case Report Form (CRF).

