7.1 Birinapant

7.1.1 Safety Consideration When Administering Birinapant

7.1.2 Dose Adjustments

Dose adjustments are allowed during both the dose escalation and the expansion phase of the study. Patients that have a DLT as defined in Section 6.2 may have their treatment held or will

incur up to 2 dose level reductions, as indicated in Section 7.1.3. If an AE that fulfills DLT criteria recurs, treatment will be held as noted below and resumed at 1 dose level lower. If a third AE fulfilling DLT criteria occurs, treatment with birinapant will be permanently discontinued, but IMRRT may be continued, provided in-field radiation toxicity is not limiting. Patients that are retreated at a lower dose level than initially assigned will not be included in the assessment of DLTs for that lower dose level (with the exception of level -1 dose) but will be included in the analysis of secondary endpoints.

In case of grade 4 non-hematologic toxicity or any grade 3 toxicity not returning to \leq grade 1 after 2 weeks of supportive care, patients will be taken off birinapant treatment and may continue with IMRRT only. Patients who experience a DLT related to the combination at a specific dose level will have both their treatments held (both birinapant and IMRRT) for up to 2 weeks and supportive measures will be implemented to ameliorate the AE. Once the AE is \leq grade 1, treatment with birinapant will be resumed at 1 dose level lower. In case of concurrent elevation of AST/ALT $>$ 3 times the upper limit of normal and bilirubin $>$ 2 times the upper limit of normal (i.e., Hy's law), study treatment will be permanently discontinued.

Dose adjustments are allowed during the expansion part of the study according to the guidelines below, with dose levels defined as follows:

Dose Level	Birinapant (mg/m ²)
-1	2.8
1	5.6
2	11
3	17
4	24

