9.4 Analysis of Secondary Endpoints

1. Overall Response is the best response by RECIST 1.1 criteria recorded from the start of the treatment until response assessment by PET-CT at 3 months post treatment as below. Estimates of response rates, local control, PFS and OS will be determined at the MTD level, including the expansion cohort. Each of these will be presented along with a 95% two-sided confidence interval appropriate to the outcome measure. For example, the PFS and OS will have confidence intervals presented for the median times.

2. FADD/ BIRC2 Copy Number Variation will be evaluated as a secondary endpoint to estimate if recurrent HNSCC are enriched for these alterations associated with worse prognosis and associated with response to birinapant and IMRRT. A bioinformatics analysis algorithm has been established for determination of copy number variation and somatic mutation calling, by comparison and validation with DNA from matched blood (13). Archived tumor samples will be subjected to exome sequencing to estimate copy number variations, from all evaluable patients.

Results will be classified according to whether they have a FADD and/or BIRC2 copy gain (more than 2 copies) or not (13), and this classification will be compared between patients who respond or do not respond, in a descriptive fashion. A Fisher's exact test will be used to provide a p-value to help interpret the potential importance of any association, but in the context of a limited size evaluation. The association between results according to whether or not they have a copy gain will be presented for OS and PFS, by comparing Kaplan-Meier curves with a two-tailed log-rank test. In addition, as exploratory analyses, the association between FADD copy gain and BIRC2 copy gain will individually be evaluated for any association with response.

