12.1.6.1.1 Evaluation of Best Overall Response

The best overall response is the best response recorded from the start of the treatment until disease progression/recurrence (taking as reference for progressive disease the smallest measurements recorded since the treatment started). The patient's best response assignment will depend on the achievement of both measurement and confirmation criteria.

For Patients with Measurable Disease (i.e., Target Disease)

Target Lesions	Non-Target Lesions	New Lesions	Overall Response	Best Overall Response when Confirmation is Required*
CR	CR	No	CR	≥4 wks. Confirmation**
CR	Non-CR/Non-PD	No	PR	≥4 wks. Confirmation**
CR	Not evaluated	No	PR	
PR	Non-CR/Non-PD/not evaluated	No	PR	
SD	Non-CR/Non-PD/not evaluated	No	SD	Documented at least once ≥4 wks. from baseline**
PD	Any	Yes or No	PD	no prior SD, PR or CR
Any	PD***	Yes or No	PD	
Any	Any	Yes	PD	

* See RECIST 1.1 manuscript for further details on what is evidence of a new lesion.

** Only for non-randomized trials with response as primary endpoint.

*** In exceptional circumstances, unequivocal progression in non-target lesions may be accepted as disease progression.

Note: Patients with a global deterioration of health status requiring discontinuation of treatment without objective evidence of disease progression at that time should be reported as “*symptomatic deterioration*.” Every effort should be made to document the objective progression even after discontinuation of treatment.

For Patients with Non-Measurable Disease (i.e., Non-Target Disease)

Non-Target Lesions	New Lesions	Overall Response
CR	No	CR
Non-CR/non-PD	No	Non-CR/non-PD*
Not all evaluated	No	not evaluated
Unequivocal PD	Yes or No	PD
Any	Yes	PD

* 'Non-CR/non-PD' is preferred over 'stable disease' for non-target disease since SD is increasingly used as an endpoint for assessment of efficacy in some trials so to assign this category when no lesions can be measured is not advised

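### The response rate leaves out treated patients who are never re-evaluated, and Sections 9.4 and 12.1.6.1.1 close best response at different times

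*Combined protocol and SAP*

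**What the plan says.** **Denominator.** Under Section 12.1.1, only patients with measurable disease at baseline who "have received at least one cycle of therapy, and have had their disease re-evaluated will be considered evaluable for response". A note in that section also keeps patients with objective progression before the end of cycle 1. This is the only definition of a response set in the documents. Section 9.4 says: "Estimates of response rates, local control, PFS and OS will be determined at the MTD level, including the expansion cohort". It asks for a 95% interval but does not say how a treated patient without an assessment is counted.

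**Related text.** Section 7.1.2 says of patients re-treated at a lower dose level that they are left out of the DLT assessment for that level, "but will be included in the analysis of secondary endpoints"; it does not mention unassessed patients. For symptomatic deterioration without objective progression, Section 12.1.6.1.1 says: "Every effort should be made to document the objective progression even after discontinuation of treatment". Under Section 6.6, patients who do not attend follow-up visits are contacted by phone or e-mail.

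**Timing.** Section 6 says: "Treatment will be delivered in 2 cycles, lasting 3 weeks each". Section 11 (footnote h) schedules the first post-baseline tumor measurement 3 months after radiation, with a window of 2 weeks either way, and none during treatment.

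**Window.** Section 9.4 defines overall response as the "best response by RECIST 1.1 criteria recorded from the start of the treatment until response assessment by PET-CT at 3 months post treatment". Section 12.1.6.1.1 says: "The best overall response is the best response recorded from the start of the treatment until disease progression/recurrence". Scans continue to 24 months.

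**The concern.** Section 3.1.12 already requires measurable disease at entry. Exclusions from the response set therefore come almost entirely from what happens after treatment starts: receiving less than one cycle, or not being re-evaluated. A patient who dies, withdraws or deteriorates without a re-evaluation leaves the denominator and could not have been in the numerator, so the reported rate can only stay the same or rise.

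The one-cycle condition is less clear in direction. It could remove a re-imaged responder who stopped early. It is also undefined for patients who stop the drug but not the radiation. For certain toxicities Section 6.5 says: "The patient may continue with IMRRT but will be taken off birinapant". The documents do not say whether radiation alone counts towards a cycle of therapy.

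The window conflict is a separate problem. A patient with stable disease at 3 months and a first response at 6 months is a non-responder under Section 9.4 and a responder under Section 12.1.6.1.1.

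Response rate is the first-listed secondary objective. The same classification feeds the responder versus non-responder comparisons in Sections 9.4 and 9.5. Two analysts following the plan could report different rates from the same data.

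**Working it through.** **What the plan gives.** Section 9.2 assumes 16 patients at the MTD, that is 6 + 10. It gives no target response rate, no precision for the rate and no expected number of non-evaluable patients, so there is no stated response figure to reproduce. The power statement for 16 patients does reproduce with exact t-test calculations at 0.01 two-sided: 83.5% for the paired comparison (effect size 1.0) and 82.6% for 8 versus 8 (effect size 2.0).

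**General effect.** If k of 16 are never re-evaluated, the reported rate equals the all-treated rate times 16/(16-k): 1.07 for k = 1, 1.14 for k = 2, 1.33 for k = 4 and 1.60 for k = 6.

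**A range for k, deaths only.** Assumptions: exponential survival, and no unscheduled scan or caliper re-evaluation before death.

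- Time to first scheduled scan: 42/30.44 + 3 = 4.38 months.
- Share dead by then: 1 - 0.5^(4.38/median).

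| Survival input | Median (months) | Share dead | Of 16 |
|---|---|---|---|
| Lower end of 8-28 months, Section 2.4, read as a median | 8 | 31.6% | 5.05 |
| Matched to 38% 2-year OS, Section 2.4 | 24 × ln 2 / (-ln 0.38) = 17.2 | 16.2% | 2.59 |
| Matched to 15% 2-year OS, Section 2.4 | 8.8 | 29.3% | 4.68 |

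The 2-week scan window moves the first row to 28.8-34.3% and the second to 14.6-17.7%. In whole patients this is about 3 to 5 of 16, with factors 16/13 = 1.23 and 16/11 = 1.45.

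Two other figures in the documents widen the range. A 28-month median gives about 10%, but under this model it implies 55% 2-year OS, outside the 15-38% of Section 2.4. The 3-6 month median in Section 6.2 gives 40-64%, about 6 to 10 of 16.

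**Effect on the rate**, with 5 responders assumed and exact (Clopper-Pearson) 95% intervals:

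| Denominator | Rate | 95% CI |
|---|---|---|
| All treated, 5/16 | 31% | 11-59 |
| 3 unassessed, 5/13 | 38% | 14-68 |
| 5 unassessed, 5/11 | 45% | 17-77 |

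**Opposite case.** Suppose one re-imaged responder is excluded for receiving under one cycle. If nobody is unassessed, the rate falls to 4/15 = 27%. With R responders of 16 and u never re-evaluated, the reported rate (R-1)/(15-u) exceeds R/16 when u > 16/R - 1. For R = 5 this is u > 2.2: 4/13 = 30.8% at u = 2 is still below 31.3%, and 4/12 = 33.3% at u = 3 is above it.

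**Window.** Each first response after the 3-month scan changes the all-treated rate by 1/16, about 6 percentage points. Closing at 3 months can only lower the rate, or leave it unchanged, relative to Section 12.1.6.1.1.

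**The case against.** Section 9.4 does not cite Section 12.1.1, so one could say that it simply names no denominator. That is a fair description, but 12.1.1 is the only rule available and is explicitly restrictive, so an analyst would apply it.

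Several provisions would recover some patients. Symptomatic deterioration is reported as such. Section 10.3.3 asks for evidence, which may be radiological, when a death is attributed to progression. Caliper measurement of superficial lesions is allowed, so re-evaluation is not limited to the scheduled scan. These points stand and make the death-based figures an upper bound for deaths, given the survival assumed. None of them brings back a patient with no re-evaluation at all.

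The magnitude is soft. A constant hazard from day 1 may overstate early deaths in patients selected for performance status and organ function. Rounding 2.59 up to 3 moves the lower factor from 16/13.41 = 1.19 to 1.23. The survival inputs are a choice among the documents' figures, and the intervals overlap widely. If non-evaluable patients are replaced, the number treated at the MTD need not be 16. All of this limits the size claimed, but the mechanism remains.

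On the window, Section 9.4 is the study-specific definition and 12.1.6.1.1 sits in generic RECIST text, so many readers would follow 9.4. Both are current text, however, and neither says which governs.

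Finally, response is secondary and descriptive, with no decision rule attached, and evaluable-set rates are common in phase I. That limits the weight of the point. It does not justify making the evaluable set the only analysis.

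**Conclusion.** Both parts hold. As written, the plan drops treated patients who are never re-evaluated and offers no all-treated rate. Upward bias is the expected net direction but not a certainty, because excluding a re-imaged responder with under one cycle would act the other way. The size cannot be fixed from the documents. A factor of about 1.2 to 1.45 is an illustration that rests on 16 patients, exponential survival, the Section 2.4 survival figures and no re-evaluation before death. Any such re-evaluation shrinks it.

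The window conflict is certain from the text, but the number of patients it would affect is unknown. No direction of bias is claimed for the marker comparisons. The DLT and MTD determination, sample size, stated power, PFS and OS are unaffected. The point should be corrected before analysis, in proportion to a secondary, descriptive endpoint.

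**What to change.** - In Section 9.4, make the main response rate at the MTD the proportion among all patients with at least one birinapant dose and measurable disease at baseline. Count patients with no post-baseline assessment as non-responders and report how many there are. This set still omits anyone who received radiation on Day 1 but no birinapant.
- Keep the Section 12.1.1 evaluable set as a supportive analysis, and say there whether radiation alone counts towards one cycle of therapy.
- Use one best-response window in Sections 9.4 and 12.1.6.1.1, for example the 3-month window, with later best response reported descriptively.
- State which set the responder versus non-responder marker comparisons use. Showing them on the other set as a sensitivity analysis is useful but not essential.

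The cost is wording in Sections 9.4, 12.1.1 and 12.1.6.1.1. No new data are needed. The reported response rate may be somewhat less favourable.

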12.1.2 Disease Parameters

Measurable disease. Measurable lesions are defined as those that can be accurately measured in at least one dimension (longest diameter to be recorded) as ≥ 20 mm (≥ 2 cm) by chest x-ray or as ≥ 10 mm (≥ 1 cm) with CT scan, MRI, or calipers by clinical exam. All tumor measurements must be recorded in millimeters (or decimal fractions of centimeters).

Note: Tumor lesions that are situated in a previously irradiated area might or might not be considered measurable. *If the investigator thinks it appropriate to include them, the conditions under which such lesions should be considered must be defined in the protocol.*

Malignant lymph nodes. To be considered pathologically enlarged and measurable, a lymph node must be ≥ 15 mm (≥ 1.5 cm) in short axis when assessed by CT scan (CT scan slice thickness recommended to be no greater than 5 mm [0.5 cm]). At baseline and in follow-up, only the short axis will be measured and followed.

Non-measurable disease. All other lesions (or sites of disease), including small lesions (longest diameter <10 mm [<1 cm] or pathological lymph nodes with ≥ 10 to <15 mm [≥ 1 to <1.5 cm] short axis), are considered non-measurable disease. Bone lesions, leptomeningeal disease, ascites, pleural/pericardial effusions, lymphangitis cutis/pulmonitis, inflammatory breast disease, and abdominal masses (not followed by CT or MRI), are considered as non-measurable.

Note: Cystic lesions that meet the criteria for radiographically defined simple cysts should not be considered as malignant lesions (neither measurable nor non-measurable) since they are, by definition, simple cysts.

‘Cystic lesions’ thought to represent cystic metastases can be considered as measurable lesions, if they meet the definition of measurability described above. However, if non-cystic lesions are present in the same patient, these are preferred for selection as target lesions.

Target lesions. All measurable lesions up to a maximum of 2 lesions per organ and 5 lesions in total, representative of all involved organs, should be identified as **target lesions** and recorded and measured at baseline. Target lesions should be selected on the basis of their size (lesions with the longest diameter), be representative of all involved organs, but in addition should be those that lend themselves to reproducible repeated measurements. It may be the case that, on occasion, the largest lesion does not lend itself to reproducible measurement in which circumstance the next largest lesion which can be measured reproducibly should be selected. A sum of the diameters (longest for non-nodal lesions, short axis for nodal lesions) for all target lesions will be calculated and reported as the baseline sum diameters. If lymph nodes are to be included in the sum, then only the short axis is added into the sum. The baseline sum diameters will be used as reference to further characterize any objective tumor regression in the measurable dimension of the disease.

Non-target lesions. All other lesions (or sites of disease) including any measurable lesions over and above the 5 target lesions should be identified as **non-target lesions** and should also be recorded at baseline. Measurements of these lesions are not required, but the presence, absence, or in rare cases unequivocal progression of each should be noted throughout follow-up.

12.1.3 Methods for Evaluation of Measurable Disease

All measurements should be taken and recorded in metric notation using a ruler or calipers. All baseline evaluations should be performed as closely as possible to the beginning of treatment and never more than 4 weeks before the beginning of the treatment.

The same method of assessment and the same technique should be used to characterize each identified and reported lesion at baseline and during follow-up. Imaging-based evaluation is preferred to evaluation by clinical examination unless the lesion(s) being followed cannot be imaged but are assessable by clinical exam.

Clinical lesions: Clinical lesions will only be considered measurable when they are superficial (e.g., skin nodules and palpable lymph nodes) and ≥ 10 mm (≥ 1 cm) diameter as assessed using calipers (e.g., skin nodules). In the case of skin lesions, documentation by color photography, including a ruler to estimate the size of the lesion, is recommended.

Conventional CT: This guideline has defined measurability of lesions on CT scan based on the assumption that CT slice thickness is 5 mm (0.5 cm) or less. If CT scans have slice

thickness greater than 5 mm (0.5 cm), the minimum size for a measurable lesion should be twice the slice thickness.

Conventional MRI: MRI may be substituted for contrast enhanced CT for some sites, but not lung. The minimum size for measurability is the same as for CT (10 mm), as long as the scans are performed with slice thickness of 5mm and no gap. In the event the MRI is performed with thicker slices, the size of a measurable lesion at baseline should be two times the slice thickness. In the event there are inter-slice gaps, this also needs to be considered in determining the size of measurable lesions at baseline.

As with CT, if an MRI is performed, the technical specifications of the scanning sequences used should be optimized for the evaluation of the type and site of disease. Furthermore, as with CT, the modality used at follow-up should be the same as was used at baseline and the lesions should be measured/assessed on the same pulse sequence. Ideally, the same type of scanner should be used and the image acquisition protocol should be followed as closely as possible to prior scans. Body scans should be performed with breath-hold scanning techniques, if possible.

PET-CT: At present, the low dose or attenuation correction CT portion of a combined PET-CT is not always of optimal diagnostic CT quality for use with RECIST measurements. However, if the site can document that the CT performed as part of a PET-CT is of identical diagnostic quality to a diagnostic CT (with IV and oral contrast), then the CT portion of the PET-CT can be used for RECIST measurements and can be used interchangeably with conventional CT in accurately measuring cancer lesions over time. Note, however, that the PET portion of the CT introduces additional data which may bias an investigator if it is not routinely or serially performed.

FDG-PET While FDG-PET response assessments need additional study, it is sometimes reasonable to incorporate the use of FDG-PET scanning to complement CT scanning in assessment of progression (particularly possible 'new' disease). New lesions on the basis of FDG-PET imaging can be identified according to the following algorithm:

- a. Negative FDG-PET at baseline, with a positive FDG-PET at follow-up is a sign of PD based on a new lesion.
- b. No FDG-PET at baseline and a positive FDG-PET at follow-up: If the positive FDG-PET at follow-up corresponds to a new site of disease confirmed by CT, this is PD. If the positive FDG-PET at follow-up is not confirmed as a new site of disease on CT, additional follow-up CT scans are needed to determine if there is truly progression occurring at that site (if so, the date of PD will be the date of the initial abnormal FDG-PET scan). If the positive FDG-PET at follow-up corresponds to a pre-existing site of disease on CT that is not progressing on the basis of the anatomic images, this is not PD.
- c. FDG-PET may be used to upgrade a response to a CR in a manner similar to a biopsy in cases where a residual radiographic abnormality is thought to represent fibrosis or scarring. The use of FDG-PET in this circumstance should be prospectively described in the protocol and supported by disease-specific medical literature for the indication. However, it must be acknowledged that both approaches may lead to false positive CR due to limitations of FDG-PET and biopsy resolution/sensitivity.

Note: A 'positive' FDG-PET scan lesion means one which is FDG avid with an uptake

greater than twice that of the surrounding tissue on the attenuation corrected image.

